5.3 Exclusion Criteria

Subjects may not be enrolled in the study if:

1. They are not a candidate for standard of care surgery based on opinion of the surgeon, anesthesiologist, or other consulting physician.
2. They have a known allergy or reaction to ICG, other radiographic contrast agent, or any component of VGT-309.
3. They have congenital long QT syndrome or $QTcF > 470$ ms by history or at Screening ECG.
4. They have received chemotherapy or immunotherapy within 4 weeks prior to study enrollment.
5. They are prisoners, institutionalized individuals, or are unable to consent for themselves.
6. They have any other co-morbidity or habit that the Investigator believes will interfere with their ability to comply with and complete the study.

5.4 Replacement of Subjects

Subjects who withdraw consent prior to receiving VGT-309 will be replaced. Subjects not meeting the evaluable criteria (see Section 5.1) *may* be replaced. Additional subjects may be added if determined necessary to adequately evaluate safety and efficacy.

6. STUDY PROCEDURES

Refer to Attachment A: Schedule of Assessments

6.1 Study Visits

Up to 3 in-clinic/hospital visits and 2 follow up visits in clinic and/or via telehealth are planned for this study. Additional visits may be added if follow up for an adverse event is needed or if screening cannot take place in a single visit. Investigators should schedule visits within the protocol-specified timelines unless they receive permission from Vergent, or unforeseeable events prevent the subject from complying.

For a complete schedule of study procedures, refer to the Schedule of Assessments presented in Attachment A. All study procedures must be recorded in source documentation (primary occurrence of a record) maintained by the clinical site.

6.1.1 Informed Consent

Prior to performing any study-related activities under this protocol, including screening tests and assessments, written informed consent with the IRB/HREC-approved ICF/PICF must be obtained from the subject in accordance with local practice and regulations.

All subjects must be provided either a written Informed Consent Form (ICF - US Sites) or a Participant Information and Consent Form (PICF - Australia) describing the study with sufficient information for them to make an informed decision regarding their participation. Subjects will be given the opportunity to ask questions about the study prior to participation.

A copy of the ICF/PICF, signed and dated by the subject, must be given to the subject and documented in the subject's source documentation. The original signed consent form will be retained with the study records.

NOTE: The ICF/PICF may be signed up to 30 days before Screening begins.

6.1.2 Screening (Days -30 to -1)

With 30 days of obtaining the informed consent, the following assessments will be done to establish a subject's eligibility for the study. Note: in cases where subjects have given consent for general pre-screening at the site, some of these assessments may be done by chart review.

When possible, the assessments should be done in the order listed here to avoid the demands of sample collection and ECG prior to the subject passing basic entry criteria requirements.

1. Review of eligibility requirements – inclusion and exclusion criteria.
2. Collection of demographic information and medical and surgical history, including review of prior and ongoing medications taken in the previous 30 days. Note: Specific attention should be paid to collecting information on any prior cancer and the treatment received for it, regardless of when that treatment was given.
3. Physical Exam.
4. Height and weight measurements (BMI will be calculated in the EDC).
5. Vital signs measurement (blood pressure, pulse rate, respiratory rate and oral/tympanic temperature).
6. Standard 12-lead ECG taken in triplicate (subject should be resting in a supine position for at least 5 minutes prior to the first ECG. There is no pausing between each of the 3 ECGs to be taken). (QTcF will be calculated as the ECG results are entered in the EDC.)
7. Blood sample collection for clinical chemistry, hematology and coagulation.
8. Urine sample collection for urinalysis, including microscopy.
9. In women of child-bearing potential, blood sample for serum pregnancy test.

Upon establishment of eligibility, subjects are scheduled for their VGT-309 infusion to take place 12-36 hours prior to induction of general anesthesia for their scheduled surgery.

NOTE: Screening exams may be done on Day 1 (Day of VGT-309 dosing) provided all results are available and the subject qualifies for the study prior to dosing.

6.1.3 Day 1: VGT-309 Dosing

Subjects will check in to the hospital or infusion center as scheduled. After confirming their eligibility by reviewing their medical and surgical history and concomitant medications for any changes since screening, those subjects still considered eligible will undergo the following:

1. Targeted Physical Exam (Focus on heart, lungs and any area of change since screening).
Note: changes from Screening to be recorded in Medical History section of the CRF.
2. Measurement of weight for dose calculation unless taken within the prior 7 days or if site SOPs require that the subject's weight be taken before the dose is prepared on the day of dosing).
3. Vital signs measurement (blood pressure, pulse rate, respiratory rate and oral/tympanic temperature).
4. In women of child-bearing potential, urine or serum sample for pregnancy test.
5. Blood sample for chemistry, hematology, coagulation. (**ONLY** if not done within 4 weeks prior to dosing).
6. Urine sample collection for urinalysis with microscopy (**ONLY** if not done within 4 weeks prior to admission).
7. Standard 12-lead ECG in triplicate within 10 MINUTES PRIOR to start of dosing (subject should be resting in a supine position for at least 5 minutes prior to the first ECG. There is no pausing between each of the 3 ECGs).
8. VGT-309 dosing to take place at 12-36 hours prior to induction of general anesthesia. (Refer to Section 4: Study Drug – VGT-309, for instructions on dose preparation and dosing procedures).
9. Assessment for potential adverse events begins with the start of dosing. (See Section 9.2.1.2)
10. Upon completion of dosing, VGT-309 subjects:
 - will be observed for 1 hour and queried for possible adverse events,
 - will have ECGs taken in triplicate, between 1 to 10 minutes and 30 +/- 5
 - will have vital signs taken at 30 +/- 5 minutes and 60 minutes +/- 5 minutes.

NOTE: Subjects may be allowed to leave the hospital grounds/infusion center and return prior to surgery, provided they have been observed for at least 1 hour following their dose of VGT-309 and the Investigator does not observe any concerning safety issues

6.1.4 Day 1 or 2: Surgery and Pathology

Following dosing with VGT-309, subjects will undergo planned standard of care surgical resection for their lung nodule or mass followed by pathological assessment of the resected tumor(s) and/or nodule(s) (Refer to Section 8: Efficacy Evaluations, for details).

6.1.5 Day 3 +/- 1 day: In-hospital follow up

While still hospitalized, subjects will undergo the following:

9. Targeted Physical Exam (Focus on heart, lungs and any area of change since screening).
10. Review of concomitant medications.
11. Vital signs measurement (blood pressure, pulse rate, respiratory rate and oral/tympanic temperature).
12. Blood sample for chemistry, hematology, coagulation. (See section 9.2.3 for assessment of laboratory results for adverse events).
13. Urine sample collection for urinalysis with microscopy.
14. Observation for and solicitation of adverse events.

6.1.6 Days 7-14: Telehealth or In Clinic follow up

Each subject will have a telehealth visit or return to the clinic to assess their general well-being, query for possible adverse events and any changes in their use of concomitant medications.

If a subject has a qualifying AE based on Day 3 laboratory results (See Section 9.2.3.1) the subject must have an additional blood draw to assess the course of the abnormal laboratory value. If the qualifying value does not return to the baseline value, the subject must return for an additional blood draw at the End of Study Visit.

6.1.7 Day 25 - 35: End of Study Follow up -OR- Early withdrawal

This visit may be conducted in clinic or by telehealth visit. During this visit or if the subject withdraws from the study early, the following assessments will be done:

1. Review of concomitant medications for changes since last visit.
2. Observation for and solicitation of adverse events.
3. Blood draw ONLY to assess a laboratory value that did not return to baseline after the Day 7-14 draw (See Sections 6.1.6 and 9.2.3.1)

Following completion of these assessments, subjects will be released from the study. Additional follow-up may be necessary if an SAE is reported and has not yet resolved (See Section 10.2.2 for details).

7. STOPPING THE STUDY OR EARLY WITHDRAWAL OF SUBJECT

This study may be stopped (terminated) by the Sponsor at any time and for any reason. Subjects on study at the time the study is stopped will be asked to complete all assessments in the Early Termination visit (see Attachment A).

NOTE: *The study may also be stopped or delayed by the DSC as outlined in Section 9.1.2.*

7.1 Individual Subject Withdrawal

The participation of an individual subject in the study may be terminated in the following circumstances:

1. Withdrawal of informed consent by the subject.
2. Any occurrence that, in the Investigator's opinion, makes continued participation contrary to the subject's best interests.

If an Investigator removes a subject from the study, or if a subject declines further study participation, an Early Withdrawal Visit, consisting of the assessments required at the Day 25-35 visit, will be completed as soon as possible. It will be the responsibility of the Investigator to ensure that all withdrawn subjects receive appropriate follow-up and medical care if needed.

8. EFFICACY EVALUATIONS

Intra-operative and post-operative evaluations will be used to support the efficacy endpoints of the study.

8.1 Primary Efficacy Assessments:

Intra-operatively:

- Use of white light and/or palpation followed by NIR imaging for localization of preoperatively identified lung lesion(s), potential synchronous or occult malignant lung lesion(s), and potential cancer-containing lymph nodes.

Ex vivo, in the operating room

- NIR imaging to determine proximity of fluorescence to closest resection margin.

Ex vivo pathology

- Histologic examination of resected tissues

8.2 Secondary Efficacy Assessments:

Comparison of NIR imaging, conducted both inside and outside the subject, to results of histologic examination.

8.3 Intra-operative Evaluations

During the surgery, the Surgeon/Investigator will first utilize standard surgical techniques using white light and/or palpation followed by *in situ* NIR fluorescence imaging using an NIR imaging system capable of detecting ICG for localization of the primary tumor and any potential synchronous or occult lesions and lymph nodes.

The number and location of pulmonary nodules and synchronous lesions that are visualized by standard techniques and/or by VGT-309 NIR fluorescence imaging will be recorded. Lymph nodes visualized by VGT-309 NIR fluorescence imaging will be identified and recorded by nodal station and zone.

Following extraction of any tumor/nodules, synchronous lesions, and lymph nodes, *ex vivo* NIR fluorescence imaging will take place in the operative suite prior to closing the surgical field.

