3. STUDY DESIGN

This is a Phase 2, multi-center, open-label study to evaluate the safety and efficacy of VGT-309, a tumor-targeted, activatable fluorescent imaging agent, in subjects undergoing surgery for proven or suspected cancer in the lung.

Following agreement with and signing of the informed consent, subjects will undergo screening measurements for the study within 4 weeks prior to the anticipated dosing:

1. Medical, surgical and medication history.
2. Complete physical exam, including vital signs and height
3. Weight (needed for dose calculation)
4. Chemistry, hematology, coagulation and urinalysis with microscopy clinical laboratory studies.
5. 12-lead ECG.
6. Serum pregnancy test for females of child-bearing potential.

After meeting all enrollment criteria, each subject will receive 0.32 mg/kg VGT-309 by IV administration 12-36 hours prior to surgery (refer to section VGT-309 Dosing, below). Subjects will be observed for 1 hour after dosing is completed and asked about possible treatment emergent adverse events.

Subjects will undergo surgical resection within 12-36 hours after completion of VGT-309 dosing. Measurements of efficacy will be taken during surgery and during the pathological examination of all surgical specimens. (Refer to Efficacy Endpoints and Efficacy Assessments sections).

Following surgery, subjects will be monitored for safety during their hospitalization. Between 7 to 14 and 25 to 35 days after surgery, the subjects will return to the clinic or have a telehealth visit for final safety assessments. At the last visit, if there are no adverse events requiring further follow up, subjects will then be released from the study.

If a subject chooses to withdraw from the study prior to the final visit, they will be asked to undergo a final safety assessment before their departure.

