## 9.4. Secondary Efficacy Endpoints

### 9.4.1. Definition of Secondary Efficacy Endpoints

To evaluate the sensitivity, positive predictive value (PPV), and 1-PPV of VGT-309 with NIR imaging for lesion(s) *in vivo*:

4. Sensitivity is defined as the probability that the tissue fluoresces when it is cancer, as confirmed by histology  $(TP/(TP+FN))$  \*
5. Positive predictive value (PPV) is defined as the probability that a tissue sample contains cancer on histologic exam if it fluoresces  $((TP/(TP+FP))$  \*
6. One minus Positive predictive value (1-PPV) is defined as the probability that a tissue sample does not contain cancer when it fluoresces  $((FP/(TP+FP))$  \*

\* TP = true positive, FP = false positive, FN = false negative

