### 9.4.2. Analysis Methods for Secondary Efficacy Endpoints

For the secondary endpoint analyses, sensitivity, PPV, and 1-PPV will be calculated and presented along with 95% confidence intervals for lesions and lymph nodes using *in vivo* assessments. Modeled point estimates and confidence intervals will be reported to account for the multiple dependent observations within subjects using Generalized Estimating Equations (GEE) since only between-subject observations can be modelled as independent. To account for the multiple dependent observations within a subject, the GEEs will be fit in SAS with an independent covariance matrix and binary (logit) outcomes. See Appendix 2.

Raw counts (%) will also be provided.

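### The protocol states an in vivo record only for lymph nodes that fluoresce, so in vivo node sensitivity has no defined false-negative count

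*Protocol*

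**What the plan says.** Protocol 8.3 has two adjacent recording rules for the operation. For lesions, the number and location of "pulmonary nodules and synchronous lesions that are visualized by standard techniques and/or by VGT-309 NIR fluorescence imaging will be recorded". For nodes, "Lymph nodes visualized by VGT-309 NIR fluorescence imaging will be identified and recorded by nodal station and zone". The lesion rule accepts detection by either method; the node rule mentions only a positive NIR finding.

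The secondary endpoint is defined in SAP 9.4.1 (also Protocol 2.2.2 and SAP 3.2): "Sensitivity is defined as the probability that the tissue fluoresces when it is cancer, as confirmed by histology", that is, TP/(TP+FN). Those definitions speak of lesions. Nodes enter through SAP 9.4.2, under which "sensitivity, PPV, and 1-PPV will be calculated and presented along with 95% confidence intervals for lesions and lymph nodes using" in vivo assessments. The estimates come from a logit GEE with independence working structure, with raw counts alongside. Protocol section 10 lets the SAP govern where the two documents differ.

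Other data sources are named. Protocol section 3 says "Measurements of efficacy will be taken during surgery and during the pathological examination of all surgical specimens". Protocol 8.3 also calls for ex vivo NIR imaging: "Following extraction of any tumor/nodules, synchronous lesions, and lymph nodes". Protocol 8.2 compares NIR findings inside and outside the body with histology. No readable text says how FN is ascertained or how a node in the pathology report is matched to a recorded station.

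**The concern.** Sensitivity needs the test result for every cancerous unit that was tested, including the negative ones. The stated node record is conditional on a positive test. That is enough for the lymph-node component of the primary endpoint and for PPV, which need only fluorescing nodes. It is not enough for sensitivity.

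At stake is a named secondary endpoint. The figure reported for nodes would depend on an unwritten choice about unlisted nodes, made when the pathology results are known. The GEE handles correlation within a subject; it cannot restore negatives that were never recorded. Whether a given station was imaged and dark, or not imaged, may not be recoverable after surgery.

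**Working it through.** The plan states no expected sensitivity or precision, so there is no figure to reproduce. All counts and rates below are assumptions.

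**Nodes.** Let T be cancerous nodes on the 8.3 list, M cancerous nodes found by pathology but not on the list, and m the number of those M that were imaged in vivo and stayed dark (0 ≤ m ≤ M). T and M can be observed if nodes can be matched to stations. m cannot, because absence from the list means either imaged and dark or never imaged.

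- Sensitivity among imaged nodes: T/(T+m).
- Listed nodes only: T/(T+0) = 100%, whatever m is.
- All unlisted cancerous nodes scored FN: T/(T+M), which is too low whenever m < M.

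Take 20 cancerous nodes, of which half fluoresced: T = 10, M = 10.

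| m (unlisted nodes that were imaged) | Sensitivity among imaged | Listed only | All unlisted as FN |
|---|---|---|---|
| 0 | 10/10 = 100% | 100% | 10/20 = 50% |
| 5 | 10/15 = 66.7% | 100% | 50% |
| 10 | 10/20 = 50% | 100% | 50% |

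The two right-hand columns do not move as the true value goes from 100% to 50%. If nodes are modelled on their own from the list, every outcome is positive, so the logit estimate is infinite and the planned confidence interval cannot be computed.

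Ex vivo imaging does not identify m. It is a reading on extracted tissue, SAP 9.4.2 specifies in vivo assessments, and SAP 9.5.1 treats ex vivo sensitivity as a separate exploratory endpoint.

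**Lesions.** Let s be true in vivo sensitivity and q the share of NIR-negative cancers that enter the data. Recorded sensitivity is s/(s + (1−s)q). A lesion seen by white light or palpation but dark on NIR is recorded under 8.3, so q is above zero. With s = 0.80:

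- q = 0.9: 0.80/(0.80 + 0.18) = 0.816
- q = 0.5: 0.80/(0.80 + 0.10) = 0.889
- q = 1: 0.80, no bias

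**Pooling.** SAP 9.4.2 does not say whether lesions and nodes are analysed together. With 100 cancerous lesions (s = 0.8, all retained) and the 20 nodes above, all of them imaged (m = 10) but entered from the list only, the recorded value is (80+10)/(80+20+10) = 90/110 = 0.818, against a true 90/120 = 0.750. Pooling would hide the all-positive node result without removing its effect.

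**The case against.** The strongest reply is that the denominator starts from histology. Sensitivity is conditional on confirmed cancer, all specimens go to pathology, and 8.3 does not say that its node list is exclusive or the only source. A cancerous node absent from a complete list of fluorescing nodes could then be counted as FN, and 100% would arise only if the analyst ignored pathology. This stands in part: 100% is conditional on using the list alone, and the documents do not say that they will. It does not rescue the estimate, because pathology cannot tell a dark node from one never imaged.

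A reader might infer that false negatives are lost for lesions too, and that lesion sensitivity is materially inflated. The documents do not support that. Ordinary lesion false negatives are recorded under the either-method rule. Protocol 8.1 requires white light or palpation and then NIR for lesions known before surgery; component A of the primary endpoint depends on how both methods performed on those lesions; and the ITT and Evaluable populations require the locating attempt followed by NIR. Only a cancer found by neither method might lack an explicit in vivo result, and if resected it still reaches histology.

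It is also fair that SAP Appendix 2, cited for this analysis, cannot be read, that the eCRF is not supplied, and that the table list is redacted. The SAP abbreviations include true negative and negative predictive value, which need NIR-negative tissue; this hints that negatives may be captured but does not establish it. No hypothesis test rests on sensitivity.

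**Conclusion.** The point holds for lymph nodes. On the readable text, in vivo node sensitivity is either 100% by construction (list only) or biased downward by nodes never imaged (all unlisted cancerous nodes scored FN), unless every such node was in fact imaged. Neither the size of the error nor its direction can be derived from the documents: it depends on which rule is applied and how many unlisted cancerous nodes were imaged. The 50% to 100% range is illustrative and rests on the assumed 10 and 10.

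For lesions the matter is minor and needs only a definition. The primary endpoint, PPV and 1-PPV are unaffected. The documents do not show that false negatives will be lost or that the reported sensitivity will be too high; they show that the rule is unstated and that the stated node record cannot support it. The conclusion would weaken if Appendix 2 or the eCRF already captures NIR-negative nodes and separates them from nodes not imaged. The change is worth making because in vivo status may not be recoverable later.

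**What to change.** In Protocol 8.3 and the eCRF, record the in vivo NIR result as positive, negative or not imaged for every resected nodal station and every preoperatively identified or resected lesion. This records what was done at surgery and requires no additional imaging.

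In SAP 9.4.2:

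- Define FN as histology-positive, imaged in vivo and not fluorescing, including lesions seen by neither method.
- Exclude histology-positive units that were not imaged, and report their number.
- State how nodes in the pathology report are matched to recorded stations.
- Report lesions and nodes separately.

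If surgeries are already complete and the status cannot be recovered, state before database lock that node sensitivity will be shown under both bounds, T/(T+M) and 100%, with the counts.

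The cost is a few eCRF fields and some SAP wording. The reported sensitivity may be lower.

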8.4 Post-operative Evaluations

Following completion of surgical procedures and imaging, the surgical specimen will be sent to the site's pathology laboratory for standard histological assessment of the surgical specimens.

NOTE: Pathology samples should be retained for at least one year and may be sent to a central location for additional analyses. (See Pathology Manual)

9. SAFETY EVALUATIONS

9.1 Data Safety Committee (DSC)

9.1.1 Constitution of the DSC

A Data Safety Committee will be appointed by Vergent Bioscience and will include at a minimum:

- An Independent Surgeon Reviewer
- An Independent Internist Reviewer
- The Project Statistician

9.1.2 DSC General Rules

9.1.2.1 Safety Review

The study may be paused if any of the following occur:

- Any subject experiences a Serious Adverse Event deemed to be related to the use of VGT-309.
- Any subject experiences an AE greater than Grade 2 attributed to VGT-309 in any single organ system

The DSC will evaluate these SAEs and AEs and determine whether:

- The study should continue, OR,
- The dose or time from infusion to surgery should be modified, OR,
- The protocol should be modified, OR,
- The study should be stopped.

